10.10.8.8.11. Additional Procedures for Monitoring of Potential Myocarditis or Pericarditis

Any study participant who reports acute chest pain, shortness of breath, palpitations, or any other symptom(s) that might be indicative of myocarditis or pericarditis within 4 weeks after study vaccination (Vaccination 1 or 2) must be specifically evaluated by a cardiologist for possible myocarditis or pericarditis. The same applies for any participant in whom a new ECG abnormality (compared to baseline) consistent with probable or possible myocarditis or pericarditis (as listed in Section 8.2.7) or abnormal troponin I level is observed at Visit 202 or 204.

In addition to a clinical evaluation, the following should be performed:

- ECG and
- Measurement of the troponin level

For any participant in whom a new ECG abnormality (compared to baseline) consistent with probable or possible myocarditis or pericarditis (as listed in Section 8.2.7) or abnormal troponin I level is observed at Visit 202 or 204, this should be achieved by repeating the assessments with the central vendor(s).

If myocarditis or pericarditis is suspected based upon the initial evaluation, the following should also be performed:

- Cardiac echocardiogram and/or
- Cardiac magnetic resonance study

Details of the symptoms reported, and results of the investigations performed, will be recorded in the CRF.

10.10.9. Substudy B Statistical Considerations

See Section 9 for general statistical considerations and phase specifics below.

10.10.9.1. Statistical Hypotheses

There are no statistical hypotheses in Substudy B.

10.10.9.1.1. Estimands

The estimands corresponding to the primary, secondary, and exploratory objectives are described in the table in Section 10.10.3.

10.10.9.1.2. Multiplicity Adjustment

There is no multiplicity adjustment for Substudy B as all analyses are descriptive in nature.

10.10.9.2. Analysis Sets

See Section 9.2 for defined analysis sets.

10.10.9.3. Statistical Analyses

The SAP will be developed and finalized for this phase before any analyses are performed and will describe the analyses and procedures for accounting for missing, unused, and spurious data. This section is a summary of the planned statistical analyses of the primary and secondary endpoints.

10.10.9.3.1. General Considerations

See Section 9 for general considerations of statistical analyses.

Note that, if a clear HAI result is not obtainable for any strain, neutralizing titers will replace HAI titers as the main immunogenicity endpoint for that strain.

10.10.9.3.2. Primary Endpoint(s)/Estimand(s) Analysis

Endpoint	Statistical Analysis Methods
Safety (adults 65 to 85 years of age)	• Point estimates and the associated exact 2-sided 95% CIs will be calculated using the Clopper-Pearson method for the proportion of participants reporting each event (local reactions and systemic events) for each vaccine group for up to 7 days following each vaccination.
	• Point estimates and the associated exact 2-sided 95% CIs will be calculated using the Clopper-Pearson method for the proportion of participants reporting each AE from the first vaccination to 4 weeks after the last vaccination, by vaccination group.
	• Point estimates and the associated exact 2-sided 95% CIs will be calculated using the Clopper-Pearson method for the proportion of participants reporting each SAE from the first vaccination to 6 months after the last vaccination, by vaccination group.
	• Point estimates and the associated exact 2-sided 95% CIs will be calculated using the Clopper-Pearson method for the proportion of participants reporting abnormal troponin I levels for each study vaccine at 2 days after the last vaccination.
	• Point estimates and the associated exact 2-sided 95% CIs will be calculated using the Clopper-Pearson method for the proportion of participants with new ECG abnormalities at 2 days after the last vaccination.

[figure not shown]
Endpoint	Statistical Analysis Methods		
Safety (adults 18 to 64 years of age)	• Point estimates and the associated exact 2-sided 95% CIs will be calculated using the Clopper-Pearson method for the proportion of participants reporting each event (local reactions and systemic events) for up to 7 days after vaccination.		
	• Point estimates and the associated exact 2-sided 95% CIs will be calculated using the Clopper-Pearson method for the proportion of participants reporting each AE from the first vaccination to 4 weeks after vaccination.		
	• Point estimates and the associated exact 2-sided 95% CIs will be calculated using the Clopper-Pearson method for the proportion of participants reporting each SAE from the first vaccination to 6 months after vaccination.		
	• Point estimates and the associated exact 2-sided 95% CIs will be calculated using the Clopper-Pearson method for the proportion of participants reporting abnormal troponin I levels at 2 days after vaccination.		
	• Point estimates and the associated exact 2-sided 95% CIs will be calculated using the Clopper-Pearson method for the proportion of participants with new ECG abnormalities at 2 days after vaccination.		

10.10.9.3.3. Secondary Endpoint(s)/Estimand(s) Analysis

Endpoint	Statistical Analysis Methods
Secondary immunogenicity (adults 65 to 85 years of age)	• HAI GMTs and associated 2-sided 95% CIs will be provided for each strain, by vaccine group, before Vaccination 1 and prior to Vaccination 2 (Day 21, if applicable) and at 1, 4, and 8 weeks after receipt of the last vaccination.
	• HAI GMFRs from before Vaccination 1 to Vaccination 2 (Day 21, if applicable) and to 1, 4, and 8 weeks after receipt of the last vaccination, and associated 2-sided 95% CIs, will be provided for each strain, by vaccine group.
	• The proportion of participants achieving HAI seroconversion prior to Vaccination 2 (Day 21, if applicable) and at 1, 4, and 8 weeks after receipt of the last vaccination, and the proportion of participants with HAI titers ≥1:40 before Vaccination 1 and at 1, 4, and 8 weeks after receipt of the last vaccination, and associated 2-sided Clopper-Pearson 95% CIs will be provided for each strain.
	• The proportion of participants achieving HAI seroconversion for all strains (targeted by the study vaccine) prior to Vaccination 2 (Day 21, if applicable) and at 1, 4, and 8 weeks after receipt of the last vaccination, and the proportion of participants with HAI titers ≥1:40 for all strains (targeted by the study vaccine) before Vaccinations 1 and 2 (Day 21, if applicable) and at 1, 4, and 8 weeks after receipt of the last vaccination, and associated 2-sided Clopper-Pearson 95% CIs will be provided.
Secondary immunogenicity (adults 18 to	HAI GMTs and associated 2-sided 95% CIs will be provided for each strain before vaccination and at 1, 4, and 8 weeks after receipt of vaccination.
64 years of age)	• HAI GMFRs from before vaccination to 1, 4, and 8 weeks after receipt of vaccination, and associated 2-sided 95% CIs, will be provided for each strain.
	• The proportion of participants achieving HAI seroconversion at 1, 4, and 8 weeks after receipt of vaccination, and the proportion of participants with HAI titers ≥1:40 before vaccination and at 1, 4, and 8 weeks after receipt of the vaccination, and associated 2-sided Clopper-Pearson 95% CIs, will be provided for each strain.
	• The proportion of participants achieving HAI seroconversion for all strains (targeted by the study vaccine) at 1, 4, and 8 weeks after receipt of vaccination, and the proportion of participants with HAI titers ≥1:40 for all strains (targeted by the study vaccine) before vaccination and at 1, 4, and 8 weeks after receipt of vaccination, and associated 2-sided Clopper-Pearson 95% CIs, will be provided.

10.10.9.3.4. Tertiary/Exploratory Endpoint(s)

10.10.9.3.5. Other Analyses

The data collected for study participants who report any symptom(s) that might be indicative of myocarditis or pericarditis (ECG, troponin level, cardiac echocardiogram, and/or cardiac magnetic resonance study) within 4 weeks after a study vaccination (Vaccination 1 or 2) will be summarized and listed by vaccine group.

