10.10.3. Objectives, Endpoints, and Estimands (Substudy B)

For the purposes of the study estimands:

• Seroconversion is defined as an HAI titer <1:10 prior to vaccination and ≥1:40 at the time point of interest, or an HAI titer of ≥1:10 prior to vaccination with a 4-fold rise at the time point of interest.

Objectives	Estimands	Endpoints
Primary Safety:	Primary Safety:	Primary Safety:
To describe the safety and tolerability of modRNA influenza vaccines when administered in differing vaccination schedules in adults 18 to 64 and 65 to 85 years of age	In participants receiving at least 1 dose of study intervention, the percentage of participants reporting: • Local reactions for up to 7 days following each vaccination • Systemic events for up to 7 days following each vaccination • AEs from the first vaccination to 4 weeks after the last vaccination • SAEs from the first vaccination to 6 months after the last vaccination	 Local reactions (pain at the injection site, redness, and swelling) Systemic events (fever, fatigue, headache, chills, vomiting, diarrhea, new or worsened muscle pain, and new or worsened joint pain) AEs SAEs
	The percentage of participants with: • Abnormal troponin I laboratory values 2 days after the last vaccination	Troponin I laboratory parameters detailed in Section 10.2
	The percentage of participants with: New ECG abnormalities 2 days after the last vaccination	ECG abnormalities consistent with probable or possible myocarditis or pericarditis as defined in Section 8.2.7
Secondary:	Secondary:	Secondary:
To describe the immune responses elicited by modRNA influenza vaccines when administered in differing vaccination schedules in adults 65 to 85 years of age	 In participants complying with the key protocol criteria (evaluable participants) at Day 21 (if applicable) and 1, 4, and 8 weeks after receipt of the last vaccination: HAI GMTs before Vaccination 1, prior to Vaccination 2 (Day 21, if applicable), and at 1, 4, and 8 weeks after receipt of the last vaccination HAI GMFR from before Vaccination 1 to prior to Vaccination 2 (Day 21, if applicable) and to 1, 4, and 8 weeks after receipt of the last vaccination The proportion of participants achieving HAI seroconversion for each strain prior to Vaccination 2 (Day 21, if applicable) and at 1, 4, and 8 weeks after receipt of the last vaccination 	HAI titers for each strain targeted by the study vaccine

PFIZER CONFIDENTIAL

Objectives	Estimands	Endpoints

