6.1.1.3. Adverse Events

6.1.1.3.1. Main Analysis

- Estimand: The percentage of participants reporting AEs from the first vaccination through 4 weeks after the last vaccination.
- Estimand strategy: Treatment policy (Section 2.2.1).
- Analysis set: Safety population (Section 4).
- Analysis time point: Day 1 from the first vaccination through 4 weeks after the last vaccination.
- Analysis methodology: Descriptive summary statistics.
- Intercurrent events and missing data: For participants who discontinue, all collected data will be included; missing AE dates will be imputed as described in Pfizer's Vaccine Statistics Rulebook.
- Reporting results: The number of participants with AEs from the first vaccination though 4 weeks after the last vaccination (n), proportion, and associated 2-sided Clopper-Pearson 95% CI will be presented for any AE, immediate AEs, severe AEs, related AEs, and AEs leading to withdrawal for each SOC, and each PT within each SOC, by vaccine group.

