6.1.1.5. Chemistry Laboratory Parameters

6.1.1.5.1. Abnormal Troponin I Laboratory Values

6.1.1.5.1.1. Main Analysis

- Estimand: The percentage of participants with abnormal troponin I values 2 days after the last vaccination.
- Estimand strategy: Treatment policy (Section 2.2.1).
- Analysis set: Safety population for 1-visit schedules and Vaccination 1 safety population or Vaccination 2 safety population for 2-visit schedules (Section 4).
- Analysis time point: 2 Days after the last vaccination.
- Analysis methodology: Descriptive summary statistics.
- Intercurrent events and missing data: For participants who discontinue, all collected data will be included; missing abnormal test values will be handled according to Pfizer safety rules.
- Reporting results: The number of participants with abnormal troponin I values 2 days after the last vaccination (n), proportion, and associated 2-sided Clopper-Pearson 95% CI will be presented for each test by vaccine group.

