6.1.1.6. Electrocardiograms

6.1.1.6.1. Main Analysis

- Estimand: The percentage of participants with new ECG abnormalities 2 days after the last vaccination.
- Estimand strategy: Treatment policy (Section 2.2.1).
- Analysis set: Safety population for 1-visit schedules and Vaccination 1 safety population or Vaccination 2 safety population for 2-visit schedules (Section 4).

- Analysis time point: 2 Days after the last vaccination.
- Analysis methodology: Descriptive summary statistics.
- Intercurrent events and missing data: For participants who discontinue, all collected data will be included; missing ECG values will be handled according to Pfizer safety rules.
- Reporting results: The number of participants with new ECG abnormalities (as defined in Section 3.1.1.7) 2 days after the last vaccination (n), proportion, and associated 2-sided Clopper-Pearson 95% CI will be presented by vaccine group.

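### The planned myocarditis/pericarditis work-up summary covers symptom reporters only, so repeat-test and imaging results of asymptomatic participants flagged by routine ECG or troponin I have no planned output

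*Protocol*

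**What the plan says.** Protocol 10.10.8.8.11 first requires a cardiologist's evaluation for any participant who reports chest pain, shortness of breath, palpitations or similar symptoms within 4 weeks of a study vaccination. It then opens a second route: "The same applies for any participant in whom a new ECG abnormality (compared to baseline) consistent with probable or possible myocarditis or pericarditis", or an abnormal troponin I, at a named visit. Both routes lead to clinical evaluation, ECG and troponin, with echocardiogram and/or cardiac MR if myocarditis or pericarditis is suspected. The section closes: "Details of the symptoms reported, and results of the investigations performed, will be recorded in the CRF". Protocol 10.9.8.8.11 sets the same two routes for Substudy A.

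The planned analysis of these data is in Protocol 10.10.9.3.5. It summarizes and lists, by vaccine group, "The data collected for study participants who report any symptom(s) that might be indicative of myocarditis or pericarditis" within 4 weeks after a study vaccination. Protocol 10.9.9.3.5 is worded the same way.

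The scheduled tests are analysed separately. Protocol 10.10.3 lists "Abnormal troponin I laboratory values 2 days after the last vaccination" and "New ECG abnormalities 2 days after the last vaccination" among the primary safety estimands. SAP 6.1.1.5 and 6.1.1.6 report each with an exact 95% CI by vaccine group.

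**The concern.** Two routes lead into the same work-up, and only one leads into its summary. For a participant flagged by a scheduled test and free of symptoms, the plan reports that the test was abnormal. It does not report whether the repeat was abnormal, what imaging showed, or whether the work-up was completed. A reader who sees several abnormal troponin values in a group and no myocarditis term in the AE tables cannot tell a case investigated and excluded from one never fully investigated.

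The by-group summary is also selected on symptom reporting. In Substudy B all site staff know the allocation (Protocol 10.10.6.2.2), so symptom reports are more open to differential ascertainment than the results of scheduled tests. In Substudy A this applies less: those who evaluate safety are blinded until Visit 5 (Protocol 10.9.6.2.2), which covers the scheduled ECG and troponin tests at Visits 2 and 3.

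**Working it through.** The plan states no figure on this point, so the check sets the sections side by side.

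**Step 1: who is evaluated and who is summarized.** Let S be the participants who report suggestive symptoms within 4 weeks, and F those flagged by a new ECG abnormality or abnormal troponin I at a scheduled visit.

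- Evaluated and recorded in the CRF (Protocol 10.10.8.8.11, 10.9.8.8.11): S or F.
- Summarized and listed (Protocol 10.10.9.3.5, 10.9.9.3.5): S.
- Left out: F without S. A flagged participant who also reports symptoms is in S and is covered.

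**Step 2: does the Substudy B SAP close the gap?** SAP 6.6 refers all safety analyses to 6.1, which covers local reactions, systemic events, AEs, SAEs, troponin I and ECG. None of these subsections describes a work-up summary. SAP 2.1 lists changes from the protocol's analysis plan and does not mention dropping one. The troponin output is "The number of participants with abnormal troponin I values 2 days after the last vaccination (n), proportion, and associated 2-sided Clopper-Pearson 95% CI" and the ECG output is "The number of participants with new ECG abnormalities (as defined in Section 3.1.1.7) 2 days after the last vaccination (n), proportion"; both stop at the scheduled time point. The AE output is "any AE, immediate AEs, severe AEs, related AEs, and AEs leading to withdrawal", by SOC and PT.

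**Step 3: where each type of participant appears.**

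| Participant | Initial flag in primary tables | AE/SAE tables | Repeat tests, imaging, outcome |
|---|---|---|---|
| Symptoms, no flag | Not applicable | Yes, where recorded as an AE | Summarized and listed |
| Flag and symptoms | Yes | Yes, where recorded as an AE | Summarized and listed |
| Flag, no symptoms | Yes | Confirmed diagnosis, or a recordable troponin or ECG abnormality | No planned output |

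The third column rests on Protocol 8.3.8 (a confirmed diagnosis is an AESI and must be recorded as an AE or SAE), 10.3.1 (an abnormal laboratory result that requires further diagnostic testing must be recorded as an AE) and 8.2.7 (clinically significant ECG changes may be AEs). The last column follows Protocol 10.10.9.3.5; the Substudy B SAP specifies no such output for any row.

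**Step 4: size.** Planned Substudy B enrollment is 165 + 13 × 120 = 1725 at most, all scheduled for ECG and troponin I at Visit 204. The documents give neither the expected number of flags nor the share without symptoms. The fraction of flagged work-ups left out therefore lies anywhere from 0 (every flagged participant also reports symptoms) to 1 (none does). At the upper end the summary shows no flagged work-up for a group whose primary troponin or ECG count is above zero.

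**The case against.** The strongest reply is that asymptomatic flagged participants are already well covered. Their flags are primary endpoints, reported by group whether or not there are symptoms. A confirmed case reaches the SOC/PT tables however it was found. An abnormal troponin I triggers mandatory further testing under 10.10.8.8.11, so 10.3.1 makes it an AE in its own right, and the conclusion of the work-up can appear as the AE term. For recipients of modRNA vaccine, a troponin I that is confirmed abnormal on repeat and judged related, or a new ECG abnormality that a cardiologist judges consistent with myocarditis or pericarditis, meets a stopping rule and goes to the IRC without any symptom requirement (Protocol 10.10.8.6, 10.9.8.6). Substudy A also analyses laboratory and ECG results at both 2 days and 1 week (Protocol 10.9.9.3.2), which gives a second scheduled result after a Visit 2 flag.

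All of this stands, and it limits the point. A reader might infer that everyone flagged by the routine tests is left out, or that these participants are missing from the analysis of the harm. Neither follows: flagged participants with symptoms are in the summary, and the flags and confirmed cases are tabulated. A reader might also call this the main known harm. Protocol 2.3.1 does not rank it: it lists myocarditis and pericarditis alongside anaphylaxis, as reported with BNT162b2, a different modRNA vaccine. Nor does the lack of an AESI category in SAP 6.1.1.3 mean that confirmed cases go unreported, since they appear at PT level.

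The reply does not supply an output for the repeat-test and imaging results, or for flags that resolved, were otherwise explained or were not fully worked up. An AE term does not show these, and IRC review is not a planned summary. The stopping rule itself turns on the repeat troponin, which shows that the protocol treats that result as decisive.

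**Conclusion.** The point holds in a narrow form. The stated population for the work-up summary selects on symptom reporting, although the protocol requires and records the same work-up without that condition. What lacks a planned output is the repeat-test and imaging results and the outcome of the work-up in flagged participants without symptoms. In Substudy B the SAP does not specify even the symptom-based summary. The Substudy A SAP was not available, so for Substudy A the conclusion rests on the protocol alone.

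The number affected cannot be estimated from the documents. No primary estimate, confidence interval, denominator or sample size changes. What changes is the content of the by-group cardiac summary. The change is worth making because the data are collected in any case. The conclusion assumes that the population in 10.10.9.3.5 and 10.9.9.3.5 is applied as written, and that the CRF instruction covers both routes, as its unrestricted wording indicates.

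**What to change.** In Protocol 10.10.9.3.5 and 10.9.9.3.5, define the population as all participants evaluated under 10.10.8.8.11 or 10.9.8.8.11 respectively. Show by vaccine group the trigger (symptom, ECG, troponin I; more than one may apply) and the outcome (confirmed, not confirmed, not completed), and list the repeat-test and imaging results. Add this table or listing to the Substudy B SAP. A separate AESI row in SAP 6.1.1.3 is optional.

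While editing, reconcile the visits. Protocol 10.10.8.8.11 refers to ECG or troponin findings at Visit 202 or 204, whereas the schedule in 10.10.1 places ECG and troponin sampling at screening, Visit 201 and Visit 204. The trigger categories depend on which visits can produce a flag.

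The cost is a wording change in two protocol sections and one additional table or listing from CRF data already collected. No procedure, clinical rule, endpoint or sample size is affected.

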10.10.9.4. Interim Analyses

No formal interim analysis will be conducted for this study phase. As the study is open-label to the sponsor, the sponsor will conduct unblinded reviews of the data during the course of the study for the purpose of safety assessment, dose selection, and/or supporting clinical development.

10.10.9.5. Sample Size Determination

See Section 9.5.

10.11. Appendix 11: Criteria for Allowing Inclusion of Participants With Chronic Stable HIV, HCV, or HBV Infection

Potential participants with chronic stable HIV, HCV, or HBV infection may be considered for inclusion if they fulfill the following respective criteria.

Known HIV infection

• Confirmed stable HIV disease defined as documented viral load <50 copies/mL and CD4 count >200 cells/mm³ within 6 months before enrollment, and on stable antiretroviral therapy for at least 6 months.

Known HCV infection

• History of chronic HCV with evidence of sustained virological response (defined as undetectable HCV RNA) for ≥12 weeks following HCV treatment or without evidence of HCV RNA viremia (undetectable HCV viral load).

Known HBV infection

Confirmed inactive chronic HBV infection, defined as HBsAg present for ≥6 months and the following:

- HBeAg negative, anti-HBe positive
- Serum HBV DNA <2000 IU/mL
- Persistently normal ALT and/or AST levels
- In those who have had a liver biopsy performed, findings that confirm the absence of significant necroinflammation

